5. PROTECTION OF HUMAN SUBJECTS

5A. Risks to Subjects

5A1. Human Subjects Involvement and Characteristics. For this research, the subject population will include:

Focus Groups Participants (n=32). This subject population will include Latino female adults, ages 18 to 55, from Denver, CO (n=16) and San Jose, CA (n=16). The Denver-based focus groups will allow for the initial development and qualitative feedback on the new app features prior to formative research with the California population (San Jose community). An iterative process of summarizing data will be used to achieve saturation and a thematic content analysis approach will be used to analyze the data. Eligibility criteria will be a) the ability to read and speak English or Spanish, b) female, c) consenting to inclusion in the study, and d) self-identify as Hispanic/Latina. Exclusion criteria include a) being less than 18 years of age, b) being over 55 years of age; and c) unable to speak or read English or Spanish.

Lab Usability Testing Participants (n=32). This subject population will include Latino female adults, ages 18 to 55, from Denver (n=16) and San Jose (n=16) who will validate the design approach and identify usability problems. This will be a two-staged approach with usability testers in Denver (Stage 1) and San Jose (Stage 2). The lab usability testing will consist of two rounds with eight participants per round (n=16). For each round of lab usability testing, the test scenarios will be written to mimic real-world use of the app. In the first round, we will test basic functionality, using findings to recommend immediate improvements to design. In Round 2, we will test enhanced functionality to identify and correct usability problems before the app is complete. Eligibility criteria will be a) the ability to read and speak English or Spanish, b) female, c) consenting to inclusion in the study, and d) self-identify as Hispanic/Latina. Exclusion criteria include a) being less than 18 years of age, b) being over 55 years of age; and c) unable to speak or read English or Spanish.

Field Usability Testing (Beta Testing) Participants (n=40). This subject population will include Latino female adults, ages 18 to 55, from Denver (n=20) and San Jose (n=20). This subject population will test the final prototype. The field usability test (i.e., beta test) of the fully programmed app will be conducted with Latinas who will use the app for two weeks to test the location-based services (LBS). Field usability participants will receive a one-on-one orientation which will include downloading the app onto their device and an app tutorial. After completing the field usability testing, participants will return for an individual exit interview. They will rate their satisfaction with the app with regards to design, appeal, and functionality, and complete the System Usability Scale (SUS),¹³³ a validated tool for assessing the usability of technology-based products.^{134,135} After field usability is complete, KB will validate the fixes and identify any remaining problems that must be corrected before the app is made available to users at the San Jose site. Usability outcomes will guide finalizing the app prior to launching the randomized control trial. Eligibility criteria will be a) the ability to read and speak English or Spanish, b) female, c) consenting to inclusion in the study, and d) self-identify as Hispanic/Latina. Exclusion criteria include a) being less than 18 years of age, b) being over 55 years of age; c) unable to speak or read English or Spanish; d) self-reported pregnancy; and e) responding “yes” to any item of the PAR-Q (Physical Activity Readiness Questionnaire).

Randomized Controlled Trial Participants (n=200). This subject population will include Latino female adults, ages 18 to 55, from Denver (n=100) and San Jose (n=100). The app will be evaluated in a randomized two-arm, comparative-effectiveness pre-post design. *iCaminemos Juntas!* will be compared to a free and readily available comparison app (*World Walking*) over 12 weeks. All participants will complete a pretest, a 6-week interim survey, and a 12-week post-test survey. The surveys will use validated scales to measure the primary outcomes. Eligibility criteria will be a) the ability to read and speak English or Spanish, b) female, c) consenting to inclusion in the study, and d) self-identify as Hispanic/Latina. Exclusion criteria include a) being less than 18 years of age, b) being over 55 years of age; c) unable to speak or read English or Spanish; d) self-reported pregnancy; e) responding “yes” to any item of the PAR-Q (Physical Activity Readiness Questionnaire).

5A2. Sources of Research Materials. Data from the focus groups, lab and field usability testing, and randomized trial will be collected in the form of handwritten notes, audio tapes, computer files, transcriptions, and questionnaires. Discussions will be recorded, transcribed, and analyzed using Atlas.ti[©] software. Data will be gathered from surveys used in the randomized trial. Data will be obtained specifically for research purposes and will be kept confidential with access limited to the Principal Investigator and specific project staff. All data will be kept in locked files.

5A3. Potential Risks. There are minimal risks associated with participation in this study. Participants may be hesitant or uncomfortable discussing their opinions regarding the *iCaminemos Juntas!* app. In addition, participants may not feel comfortable responding to questions about their opinions on the appeal, ease of understanding, navigation, and functionality of the app. For participants in the field usability test and randomized trial, the potential risks involved in this project include psychological and/or medical complications resulting from increasing exercise (e.g., sore muscles, etc.). There is the possibility of adverse events ranging from minor musculoskeletal problems to, in very rare cases, cardiovascular events. Occasionally study participants experience minor orthopedic problems, but most are self-correcting with rest and standard first aid. The risk should be low in this study. Fatal events during exercise are extremely rare. We have conducted numerous exercise training studies and have never had a serious adverse event. There are no anticipated risks from completing the self-report questionnaires. If signs of minor stress or fatigue are apparent, participants will be given time to take a break from completing the questionnaires. It is estimated that the questionnaires will take 30-45 minutes to complete. All participants will be allowed to withdraw if they are uncomfortable with providing any of this information. Their responses will in no way be shared with anyone except project staff. Responses to the questions will be coded to protect confidentiality, and participants may choose to not answer questions.

5B. Adequacy of Protection Against Risks

5B1. Recruitment and Informed Consent. Human Subjects oversight will be conducted by Western Institutional Review Board (WIRB; DHHS IRB Reg. No. IRB00000533) and Stanford's Institutional Review Board (IORG0000208). All consenting procedures will be IRB-approved. The IRBs will review and approve subject materials (including recruitment advertisements, letters, consent forms, survey instruments) and data management procedures prior to study implementation.

We will recruit participants primarily through mass mailings, newspaper and social media ads, and existing research participant databases. For the randomized trial, we will recruit a total of 200 currently community-dwelling Latinas; 100 from the Denver area and 100 from the San Jose area. Participants will be presented with IRB-approved consent forms that will describe the purpose of the project, risks and benefits, and selection criteria. Participation will be voluntary, with the right to stop participating at any time. No clinical data will be captured. Responses to survey questions and the discussions would not reasonably place the participants at risk of criminal or civil liability or be damaging to the participants' financial standing, employability, or reputation. All data coding, data entry, analysis and reporting activities will be conducted by KB and Stanford. Focus group and lab and field usability testing participants will read and sign IRB-approved consent forms. Randomized trial participants will consent online. Participants will be informed that they have a right to withdraw from the study at any time. No additional data will be collected from participants who decide to withdraw; however, the information collected prior to withdrawal will remain in the study. IRB-approved surveys and discussions will be carried out under the supervision of senior project staff.

5B2. Protection Against Risk. To minimize potential psychological risk, all focus group and usability testing facilitators will establish ground rules for discussion that includes an open, non-evaluative exchange of comments and ideas. All surveys and data collection forms will be approved by an IRB and employed under the supervision of senior project staff. Participants will be told that they do not have to answer any questions which make them uncomfortable and can terminate their participation at any time they wish.

Notes, surveys, audiotapes, and data will be accessible only by research personnel. Responses to survey questions would not reasonably place the subjects at risk of criminal or civil liability or be damaging to the subjects' financial standing, employability, or reputation. No clinical data will be captured. The data collected on this project will be obtained with the "use of educational tests, survey questions, [and] interview procedures."

In Phase I, we provided participants with safety tips and a resource guide based on information from National Cyber Security Alliance (www.staysafeonline.org) and National Crime Prevention Council (<http://www.ncpc.org/topics/internet-safety/social-networking-safety>). In addition to these safeguards, we worked closely with our Community Advisory Board (CAB) and Expert Advisory Board (EAB) to determine best approaches for maintaining the personal and Internet safety of our participants. For Phase II, we will utilize these same practices, but will also include multiple ID verification approaches and a security expert. Additionally, we will work with our CAB and security consultant to maintain rigorous standards for safety that are also agreeable to our users. Specifically, KB's Programming Manager will lead the app programming, will complete his certification in ethical hacking (CEH) which will allow him to assess for weaknesses and vulnerabilities in the app. His certification should be completed by late Summer 2018. [name] (President, Litchfield County Computer, LLC) will serve as a consultant and provide independent expertise on app security. [name] has a BBA in Management Information Systems with a concentration in Computer Security and is an app security expert. In addition, KB's IT Manager will be responsible for data security. He is certified with Window Servers, is a Microsoft Certified Systems Engineer (MCSE), and has continuously received an A+ rating for Network security in independent audits.

To ensure safety, all participants will be required to complete multiple ID verification approaches that are currently standard practice in other consumer areas (e.g., Airbnb). All participants will be fully informed of these privacy policies. Participants will submit a copy of their photo ID (front and back) to the study team. The study team will complete two verifications with the submitted ID: (1) the photo ID will be encrypted (ensuring privacy), submitted to the IDscan app (www.idscan.com), and a report will be delivered to the study team; and (2) the name will be entered into a publicly available, free website (www.checkingrecords.com) which accesses public record information, a social networking summary, a general online lookup, court and driving records. The study team will vet the information obtained from the ID verification for any potential concerns. If concerns arise, the study team will discuss with the participant the options for study discontinuation or continuation. All information obtained during the ID verification process will be confidential and not shared on the app. Participants will be required to consent to the ID verification. *iCaminemos Juntas!* app participants will be required to provide a profile picture to be displayed on the app (it can be different than their issued photo ID). The study team will confirm that the profile picture is similar to the ID provided during the verification process.

With regards to walking environment, the database for meeting locations will be derived in a similar manner as Phase I. Our CAB and Phase I participants rated all of the walking locations as safe. Similarly, for Phase II, exercise locations will be limited to parks, trails, schools, recreation centers, and malls (venues that are public and well-lit). To ensure users' privacy and safety, the app will serve as the "gatekeeper". Users cannot be located by another user without permission, cannot set up a meeting time that is outside the app's allowable walking hours, and cannot set up meetings to walk with an unauthorized user. Also, users cannot change a meeting location unless the new meeting location is in the database. Any changes or deviations that are made are tracked by the app. All users will be asked to rate their opinion of the walking location, its safety, and whether they agree to use the location again. If a user prefers to not use a location, that location option will be removed from their available list of locations. If a location consistently receives poor ratings, it will be removed from the database as an available location option. Throughout the project, we will work closely with our CAB and security consultant to maintain rigorous standards for safety that are also agreeable to our users.

Data will be de-identified before being submitted for analysis. All notes and printed data collection forms and questionnaires will be stored in locked cabinets at KB offices; all electronic data files will be stored on KB's secure network servers behind computer firewalls, with routine backup. All identifiers will be stored in secure files and behind computer firewalls and results will be shared in aggregate form only. All human subjects participating in this project will be 18 years and older.

To minimize the risk to participant data privacy and protection through the internet, KB programmers will monitor and maintain all programs and databases and use an established protocol for participant cyber safety and security. KB is HIPAA complaint and maintains vigorous technical safeguards which are built into KB's IT system to protect information and to control access to it. All participant information will be protected using 128-bit SSL encryption. All Internet information must travel through KB's CISCO ASA 5505 firewall using ASA software version 9.0(2) encrypted 3DES-AES. Traffic then moves to KB's web server. This server is a Dell Power Edge T-310 with 32 GB of RAM, 1.5 TB available disk space on a RAID 5 redundant drive system using Windows HyperV Operating System. The virtual web server uses Windows 2008 IIS Web server software. User click stream data is collected using Webtrends, and is saved to our SQL server. Enrollment data is transferred to our SQL server (Windows Server 2008) which uses MS SQL server 2008 R2 database software. This machine is also a Dell Power Edge T-310 with 32 GB of RAM, 1.5 TB available disk space on a RAID 5 redundant drive system using Windows HyperV OS, and has no access to the Internet. When a participant is directed to take a survey, their computer is linked to a third server in our system which is also a Dell Power Edge T-310 with 32 GB of RAM, 1.5 TB available disk space on a RAID 5 redundant drive system using Windows HyperV OS. This server runs Question Pro Survey software. Data from each survey is collected and saved to the SQL server mentioned above. All network traffic is sent from the CISCO firewall to a Syslog server using Manage Engine Firewall Analyzer 7 software. Login and network activity is required and monitored by Windows servers to an event viewer. Servers are kept in a locked room on site. All files are secured locally using MS NTFS. All traffic between servers and PCs on the LAN are digitally signed communications. Each local machine has a built-in operating system firewall. Data from the Question Pro surveys are exported for data analysis by local machines which are also behind KB's firewall. Access to this exported data by outside sources is done using File Transfer Protocol (FTP) protected by Secure Socket Layer (SSL). SQL databases are protected by the built-in security of MS Active Directory. Data is backed up using a Quantum SuperLoader 3 tape library using LTO4 tapes that contain 800 GB/1.6 TB of info (depending on compression used). The device holds 16 tapes. The backup software used by KB is Symantec Back-up Exec. 2012. Daily backups are incremental and tapes are recycled weekly. Weekly backups are done every Friday and are recycled every 6 weeks. Monthly backups are done on the last Friday of each month, and are full backups of all data. These monthly tapes are stored in a secure offsite facility and are never recycled.

With regards to app security on personal devices, Apple (e.g., iOS programmed apps) completes a full security review of any app installed on a phone including beta/testing apps through their App Transport Security (ATS).²⁰⁶ KB App programming will include all key developer-related features to ensure ATS security.²⁰⁷ Google Play (Android programming) does not conduct a similar security check; however, KB has extensive experience with developing and marketing both iOS and Android programmed apps using an established protocol (SSL/TLS: Secure Sockets Layer/Transport Security Layer) and has never experienced a data breach. All usability testers will be informed that information being sent to and from their device will remain encrypted and password protected, and at any time they are allowed to opt-out and uninstall the app.

5C. Potential Benefits of the Proposed Research to Participants and Others

Potential benefits will be the knowledge that one has helped to develop and test a smartphone app that uses location-based social networking to connect Latinas in neighborhood-specific geographic areas to promote increased walking behavior. Also, we believe that field usability testing participants and randomized trial

participants will benefit from an increase in physical activity. In addition, participants will be compensated as follows: \$25 for participation in the focus group and lab usability testing; \$50 for participation in the field usability testing, and \$100 for completing all study assessments (baseline, 6-week, and 12-week) in the randomized trial.

A description of this study will be available on <http://www.ClinicalTrials.gov>, as required by U.S. Law. This website will not include information that can identify the participant. At most, the website will include a summary of the results. This website can be searched at any time.

5D. Importance of the Knowledge to be Gained

The *iCaminemos Juntas!* app will be the first smartphone app that uses location-based social networking to promote physical activity (PA), and the only app of its kind targeted to Latinas. *iCaminemos Juntas!* will also expand upon what is known to be successful in Latina PA engagement (e.g., community-oriented, social support) while simultaneously addressing key barriers to PA (e.g., safety concerns).

5E. Multi-site Collaboration

The proposed research involving human subjects will be conducted by Klein Buendel, Inc. (FWA No. 00003715) and Stanford University, School of Medicine, The Stanford Prevention Research Center (FWA No. 00000935).

5G. Training in the Ethical Conduct of Research with Human Subjects

The Principal Investigator, Co-Investigator, and study personnel have completed the required training in the Ethical Conduct of Research with Human Subjects. Necessary documentation will be provided to NIH prior to funds being awarded.

6. Data and Safety Monitoring Plan

A data safety and monitoring plan will be implemented for this project, following well-established procedures. We will not set up an independent Data Safety and Monitoring Board because this study is low risk, does not include use of therapeutics, and psychological risk is not anticipated.

Study progress will be monitored monthly by the Principal Investigator, Project Coordinator, and Project Biostatistician. All critical events will be reviewed by the PI and Co-Investigator to ensure that our methods have not been intrusive or disruptive. The data management staff will examine the quality of data input throughout the data collection period following standard quality control and assurance procedures (e.g., double entry of hard-copy coded data; detection and estimates of keystroke errors, identification of systematic mistakes in coding or responses; range checks). Also, analyses of the data will be performed by [name] and [name] at the conclusion of the data collection period to assess distributional assumptions and the success of randomization. By having the Project Coordinator, Project Biostatistician and data management staff monitor the data, the PI's conflict of interest is reduced.

The Project Biostatistician and data management staff will attend regular project meetings with the PI, Co-Investigator, Project Coordinator, and other project staff and routinely report on the quality of the data and other outcomes of this monitoring process. Compliance with data collection protocols will be monitored throughout data collection by the PI and Project Coordinator.

The PI and Co-Investigator are responsible for reporting all adverse events to the IRBs. Only Grade 1 events are expected on this trial. Thus, adverse events will be reported annually, as required by DHHS. This report will be reviewed by KB's, and Stanford's IRB. Any action taken by the IRB or project investigators resulting in a temporary or permanent suspension of the trial will be communicated immediately by the PI to the grant program officer.

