Participants will be assisted with downloading the appropriate app, provided instructions on how to use the app (*iCaminemos Juntas!* or *World Walking*), and encouraged to use the app daily.

6-week interim assessment: Participants will complete interim assessments of initial changes. An invitation email and text messages containing a link to the interim surveys along with their unique password (PIN number) will be sent. Participants will complete the web-based surveys using either their computer or smartphone; no in-person meeting will be required. Participants who do not complete the surveys within 3 days will receive an email and text reminder (and 3 more reminders at 3-day intervals if still not completing it).

12-week post-test assessment: Participants will complete an in-person post-test assessment. They will meet individually with a study staff to complete the online surveys on a study tablet and a brief post-test interview.

3C.6.2. Outcomes: Baseline, Interim, and Post-test Measures. The baseline, 6-week interim, and 12-week post-test surveys will use validated scales to measure the primary outcome – physical activity - and secondary outcomes of social and environmental support and quality of life (QOL). Surveys should take 30-45 minutes to complete. See **Table 4** for schedule of measurements.

TABLE 4: Schedule of Measurements

Assessment	Screening	Pre-test/Baseline	Week 6	Week 12/Post-test
Inclusion Screener	X			
Physical Activity		X	X	X
Social & Environmental Support		X	X	X
Quality of Life (QOL)		X	X	X
Usage Data (iCaminemos Juntas! app only)			X	X
System Usability Scale (iCaminemos Juntas! app only)				X

Physical Activity:

The Community Healthy Activities Model Program for Seniors (CHAMPS¹⁶⁰) is a 41-item PA questionnaire that measures self-reported minutes-per-week of PA calculated as total weekly caloric expenditure in all PA. It was developed for underactive populations and validated among older adults.¹⁶⁰ However, CHAMPS has been used with younger and racially/ethnically diverse populations; it is sensitive to change specifically in Latino and other populations including ones younger than senior age.¹⁶⁴⁻¹⁶⁷ The CHAMPS asks about activities undertaken for exercise, daily activities that are physical in nature, and physically active recreational activities during “a typical week in the past 4 weeks.” CHAMPS has strong psychometric properties,^{160,168} including validation in Spanish and sensitivity to change.¹⁶⁹⁻¹⁷¹

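### A single annual IRB reporting interval covers all adverse events, with no stated route for events beyond Grade 1 and no adverse-event item listed for either arm

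*Combined protocol and SAP*

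**What the plan says.** Section 6 (Data and Safety Monitoring Plan) states the scope of the duty first: "The PI and Co-Investigator are responsible for reporting all adverse events to the IRBs". It then gives the interval and the reason for it: "Only Grade 1 events are expected on this trial. Thus, adverse events will be reported annually, as required by DHHS". The one matter it says will be communicated immediately is a suspension of the trial, and that goes to the grant program officer. The same section declines an independent monitoring board, provides for monthly review of study progress, and has the PI and Co-Investigator review critical events.

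Section 5A3 (Potential Risks) describes a wider range of harm: "There is the possibility of adverse events ranging from minor musculoskeletal problems to, in very rare cases, cardiovascular events". It adds reassurance: "Fatal events during exercise are extremely rare", and "We have conducted numerous exercise training studies and have never had a serious adverse event".

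Section 3C.6.2 contains "TABLE 4: Schedule of Measurements". Its rows are the inclusion screener, physical activity, social and environmental support, quality of life, and, for the test app alone, usage data and the System Usability Scale. Under section 3C.6.1 the week-6 contact is by web survey and "no in-person meeting will be required". At week 12, "They will meet individually with a study staff to complete the online surveys on a study tablet and a brief post-test interview".

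**The concern.** A reporting rule has to work for the event nobody expects. Here the interval for every adverse event is derived from an expectation of the mildest grade, while the risk section of the same document accepts that something worse could happen. The app also brings together women who were not previously connected (sections 3A.2 and 5B2), so an incident at a walk is a foreseeable type of event that section 6 does not address.

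There are two consequences. If section 6 is followed as written, the IRBs could learn of a serious event only at the next annual report. And if no assessment asks about injuries or incidents, what reaches the investigators depends on what participants choose to volunteer.

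**Working it through.** The plan states no figure on this point, so there is none to reproduce. The check is a comparison of the sections, with a little arithmetic for scale.

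**Reporting route**

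1. Scope (section 6): all adverse events, to the IRBs.
2. Interval (section 6): annual. The linking word makes the Grade 1 expectation the stated reason.
3. Risks acknowledged (section 5A3): musculoskeletal problems up to rare cardiovascular events.
4. Faster IRB route for anything outside the expectation: none found in section 6, section 3C.6.6 or sections 5A to 5B.
5. Nearest substitutes:
   - The critical-event review in section 6 is internal. The term is not defined, no time limit is set, and the stated purpose is to check that study methods are not intrusive or disruptive.
   - The monthly monitoring in section 6 concerns study progress.
   - Section 3C.6.6 provides for team monitoring, an expert group and referral of participants in distress, but gives no event criteria and no IRB route.
   - The PAR-Q and pregnancy exclusions (section 5A1) and the identity checks, restricted venues and hours, and location ratings (section 5B2) reduce risk. They do not report events.

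**Ascertainment**

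1. Table 4: no adverse-event row at screening, baseline, week 6 or week 12.
2. Instruments described in section 3C.6.2: CHAMPS, NEWS-A, Social Support for Exercise, SF-12 and the environmental supports questionnaire. None is described as asking about injury or incidents.
3. Week 6: web surveys only. Week 12: the same surveys plus an interview of unstated content.
4. The test app's question after a walk on whether the location was safe (app description before section 3C.3.1) rates the venue, not injury.

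**Scale**

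- Exposure: 200 × 12 / 52 = 46 person-years.
- Evaluation window: project months 10 to 24, so 24 − 10 + 1 = 15 months, which holds one or two annual reports.
- The documents give no rate for events above Grade 1. With an assumed per-participant risk p, the chance of at least one among 200 is 1 − (1 − p)^200: 18% for p = 0.1%, 63% for 0.5%, 87% for 1%. These rates are illustrations, and the conclusion does not rest on them.
- If no event were seen, the one-sided 95% upper limit on risk is 1 − 0.05^(1/n): 1.5% for n = 200, and 1.9% for n = 160 (200 less the planned 20% attrition). Either limit is meaningful only if participants were actually asked.

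**The case against.** The strongest reply is that the two safety sections can both be true. Saying that only Grade 1 events are expected does not deny that a cardiovascular event is possible. A reader might infer a flat contradiction, or that the protocol names death as a risk of this study. The documents support neither. The sentence on fatal events is a reassurance, set beside a statement that risk in this study should be low and a record of no earlier serious events.

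It can also be said that the annual interval is meant for the expected events, and that the IRBs' own procedures would govern a serious one. That is a fair reading of intent, but the text does not say so, and its scope sentence covers all adverse events. A reader should equally not infer that a serious event certainly would wait a year. What can be shown is that no quicker route is written down.

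The safeguards in sections 3C.6.6, 5A1, 5B2 and 6 are real and should be credited. This is a low-risk walking study with screening at entry and considerable attention to personal safety. They lower the chance of an event without saying how one is reported.

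On ascertainment, Table 4 is a schedule of outcome measurements and the week-12 interview might ask about harm. It is therefore not established that no visit asks, only that no such item is listed. A reader might go further and infer that harms are detected unequally between arms. The evidence for that is weak: the test app's location question rates meeting places, the comparator arranges no meetings to rate, both arms complete neighborhood-safety instruments, and comparing harms is not a stated aim.

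**Conclusion.** The point stands as a gap in the written safety plan, and it should be corrected. One annual interval is applied to all adverse events on the strength of an expectation that does not cover the rare cardiovascular events acknowledged in section 5A3, or an incident at an arranged walk. No IRB route is stated for events outside that expectation, and no adverse-event item is listed for either arm.

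The size is that of an oversight gap in a low-risk study of 200 women followed for 12 weeks each. No event count or actual delay can be derived from the documents.

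The conclusion assumes that section 6 is the operative reporting rule and that no further safety document alters it. It does not depend on whether annual reporting meets the DHHS requirement that the plan cites, which cannot be checked from the documents.

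**What to change.** - Reconcile sections 5A3 and 6. Confine the annual summary to the expected Grade 1 events, and state that any other event, including a personal-safety incident at a walk, goes to both IRBs under their own prompt-reporting procedures. The documents do not describe those procedures, so the text should refer to them rather than set a new timetable.
- In section 6, define critical events and say how the internal review leads to IRB reporting.
- Add the same short injury and safety-incident items to the existing 6- and 12-week surveys in both arms, and list them as a row in Table 4. If the week-12 interview is meant to cover this, say so.

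The cost is protocol wording and two or three survey items, so a slightly longer survey and no extra visits. One limit remains: section 5B1 stops data collection at withdrawal, so the survey items will not reach a woman who withdraws. The reporting wording should therefore also cover events learned of at withdrawal.
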